The stratified analyses mentioned in this SAP will be conducted in consideration of the randomization stratification factors region, eGFR category, type of albuminuria and history of cardiovascular disease (CVD) unless specified otherwise, see also section 4.5.4. The strata variables type of albuminuria, eGFR category and history of cardiovascular disease used in the statistical analysis will be based on the screening UACR and eGFR assessments and medical history and corrected via the interactive voice/web response system (IxRS) if necessary. All subjects will be analyzed according to their correct stratification category. If screening values are not available, the run-in values will be used. If a subject's actual UACR / eGFR combination results in a stratification group that does not exist in the study (e.g. in 17530, very high albuminuria and eGFR ≥ 45 to < 60 mL/min/1.73m²) then the stratification group the investigator originally specified in IxRS will be kept.

In case of stratification errors, the primary analysis will also be repeated based on the stratification category used in the randomization as a sensitivity analysis.

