4.5.3 Other data handling

Only the data provided by the central laboratory will be used for analysis, values from local laboratories will not be used in the statistical analysis and will be listed only unless there are no values from the central laboratory available for baseline.

In case of retests for Run-in and Screening visits, the closest measurement prior to randomization will be used for analysis instead of the scheduled measurements. At all visits starting at Visit 1 and if not stated otherwise, only the values at scheduled measurements will

be used for analysis. In the unexpected case that more values than planned are available for a scheduled visit, only the first valid value will be used.

For the derived visit “Any time post-baseline” (applicable for efficacy) this will include any measurement after date of randomization, including unscheduled assessments. For the derived visit “Any treatment-emergent” (applicable for safety), only assessments on or after study medication start date until 3 days after the date of any temporary or permanent interruption of study drug, including unscheduled assessments, will be considered.

For those laboratory values which are <LLOQ (Lower limit of quantification), half the value of the LLOQ will be used for analysis. Differences between 2 values <LLOQ will be assigned values of 0. Ratios between 2 values <LLOQ will be assigned a value of 1. For values which are >ULOQ (Upper limit of quantification), the ULOQ will be used for analysis. This rule does not apply to the finerenone plasma concentration data.

In case of log-normally distributed data, descriptive statistics other than minimum, maximum and median will only be calculated if at least 2/3 of the individual data were measured and were above the lower limit of quantification. In tables showing descriptive statistics, where values below LLOQ are included, these descriptive statistics will be marked.

Urinalysis is assessed 3 times per visit. UACR will be determined 3 times at each visit from first morning void urine samples collected on 3 consecutive days. For the analyses of UACR, the 3 measurements at one visit will be combined provided that at least 2 measurements are available. First, the coefficient of variation (CV) will be calculated for the 3 values as follows considering the log-normal distribution for UACR [7]:

$$CV = \sqrt{\exp(SD_{\ln}^2) - 1},$$

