where SD_{\ln} is the standard deviation of the 3 log-transformed UACR values. If the coefficient of variation exceeds 25%, the median from the measurements will be used for the analyses. The median in case of an even number of values will be defined as the geometric mean from the 2 middle values. If the coefficient of variation is 25% at the most, the geometric mean will be used. If 2 or all 3 scheduled assessments are missing or invalid and unscheduled assessments have been performed, then the set of unscheduled measurements closest to the planned visit will be used to determine the UACR at the respective visit if performed within 30 days before or after the planned time point for all visits from Visit 3 (Month 4) onwards (with the following exception: only samples with 2/3 of values no later than 30 days (for “last on-treatment” analysis) or 3 days (for “last treatment-emergent” analysis) after last study drug intake will be considered). For Visit 1, 2 out of 3 samples have to be on or before the day of randomization and have to lead to non-missing values in order for the set of samples to be valid for baseline calculation; otherwise (also including the case when there is one valid sample at Visit 1), the set of screening samples will be considered for baseline.

In the case of ESRD, the UACR and eGFR values after the onset date of ESRD will be excluded from all efficacy analyses, but included in the safety analyses.

For the stratification group type of albuminuria at screening (high or very high), the classification supplied from the central lab via IxRS will be used. The rule that has been applied by the central lab for this classification is, if there are 3 values, the median value

should be taken; if 2 values, then the arithmetic mean value, regardless of degree of variation between the values. The lab reports from the run-in and screening visits will include the type of albuminuria, to assist the investigators in reducing stratification and randomization errors.

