- Hospitalization events will be counted up to the day of withdrawal from the study or death. Randomized subjects without a hospitalization event at the time of analysis will be censored at the date of their last contact up to and including the EOS visit or date of death.
- All-cause mortality will be counted up to the last date vital status could be obtained. Randomized subjects without such an event at the time of analysis will be censored at the last date vital status could be obtained up to and including the EOS visit.

An ANCOVA model will be fitted to the logarithmized ratios of UACR at Month 4 to UACR at baseline including the factors treatment group, the stratification factors region, type of albuminuria, eGFR category and history of CVD and the logarithmized baseline UACR as covariate. Corresponding two-sided 95% confidence intervals will be computed. As the baseline UACR defines the type of albuminuria, the log-transformed baseline UACR will be nested as covariate in type of albuminuria.

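### The Month 4 UACR ANCOVA uses the Screening UACR set almost only as a two-level stratum, leaving a modest amount of precision unused

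*SAP*

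**What the plan says.** SAP 6.2.2.1 models the log ratio of Month 4 to baseline UACR with treatment group, "the stratification factors region, type of albuminuria, eGFR category and history of CVD and the logarithmized baseline UACR as covariate". It adds: "As the baseline UACR defines the type of albuminuria, the log-transformed baseline UACR will be nested as covariate in type of albuminuria". Protocol 10.3.3.3 lists the same covariates, without the nesting, and gives consistency with the primary analysis of Phase II Study 16243 as its reason.

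Two different sample sets feed this model. Under SAP 4.5.3, "UACR will be determined 3 times at each visit from first morning void urine samples collected on 3 consecutive days". For baseline, the Visit 1 set is used if "2 out of 3 samples have to be on or before the day of randomization" and give non-missing values; otherwise the Screening set takes its place. The stratum comes from Screening: SAP 4.1 says that the strata variables "will be based on the screening UACR and eGFR assessments and medical history", and SAP 4.5.3 says "For the stratification group type of albuminuria at screening (high or very high), the classification supplied from the central lab via IxRS will be used". That laboratory's rule there is "if there are 3 values, the median value" (the arithmetic mean if there are two), which is then classed as high or very high.

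No section uses screening UACR as a continuous covariate. The UACR mixed model (SAP 6.2.3.2) and the imputation code (SAP Appendix B) also carry only log baseline UACR and the strata.

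**The concern.** The protocol itself calls UACR highly variable (section 6.4.2.2), and the SAP takes three samples per visit with a special rule when they disagree. One visit's set is therefore an imperfect measure of a patient's pre-treatment level. A second pre-randomization set exists for nearly everyone, because entry requires UACR at Screening (Protocol 6.1) and a missing value there is a per-protocol validity finding (SAP 5.3). Reducing that set to one cut at 300 mg/g discards most of what it adds.

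The SAP's stated reason for nesting treats the two sets as one. Yet SAP 4.5.4 lists type of albuminuria at screening and at baseline as separate subgroups, and the baseline version has an extra normal level. The plan thus expects them to differ.

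What is at stake is precision for one secondary endpoint, its exploratory subgroup estimates and its imputation model. Bias and type I error are not in question.

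**Working it through.** **1. The plan's own figures.** The documents give no SD, residual variance or power for UACR. The one figure attached to this test is the final two-sided level of 0.04967388 (SAP 4.7). A two-look bivariate normal integral (correlation √(2/3), first look at two-sided p < 0.00270, overall 5%) gives 0.049674, so it reproduces.

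**2. Timing.** Screening is at most 2 weeks before Visit 1. Protocol Table 9-1, footnote c, allows Screening samples ±7 days around that visit and Visit 1 samples within 7 days before it. The sets can be nearly adjacent or up to about 14 + 7 = 21 days apart.

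**3. Gain by formula.** Let r12 be the correlation of log UACR between Screening and Visit 1, and r1 and r2 the correlations of Visit 1 and Screening with Month 4. All are assumptions. The proportional cut in residual variance from adding Screening is

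(r2 − r1·r12)² / [(1 − r12²)(1 − r1²)].

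| r12 | r1 | r2 | Cut |
|---|---|---|---|
| 0.85 | 0.80 | 0.78 | 10.0% |
| 0.85 | 0.80 | 0.76 | 6.4% |
| 0.90 | 0.85 | 0.82 | 5.7% |
| 0.90 | 0.80 | 0.78 | 0.0036/0.0684 = 5.3% |
| 0.90 | 0.80 | 0.75 | 0.0009/0.0684 = 1.3% |
| 0.95 | 0.80 | 0.78 | 1.1% |
| 0.90 | 0.80 | 0.72 | 0 |

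In the last row r2 = r1·r12, which is simple decay over time. If all three correlations equal r, the residual goes from 1 − r² to 1 − 2r²/(1 + r): a cut of 17% at r = 0.7 and 22% at r = 0.9. None of these rows accounts for the screening-based stratum already in the model.

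**4. Gain with the SAP model simulated.** Screening, Visit 1 and Month 4 were simulated with three samples each, the SAP 4.5.3 combining rule, the entry limits (30 to 5000 mg/g), the stratum from the screening median, and log baseline nested in it. Region, eGFR category and CVD history were left out. Assumed on the log scale: visit-level SD 0.15-0.45, day-to-day SD 0.3, SD of true change 0.2-0.6, and correlation between Screening and Visit 1 deviations 0-0.8.

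These give log-ratio SDs of 0.40-0.92. As a plausibility check, the Phase II shares with at least 30% and 50% decreases (Protocol 3.3) imply, under normality, SD = (ln 0.70 − ln 0.50)/(z₃₀ − z₅₀). This is 0.87 on placebo (23.9%, 13.6%), 0.40 at 10 mg (46.0%, 17.2%) and 0.59 at 20 mg (62.5%, 40.2%).

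- The cut in residual variance was 2.8% to 15.3% over 36 scenarios, and 5.6% to 13.9% where the log-ratio SD was about 0.6.
- Example (visit SD 0.25, change SD 0.4): 0.344 falls to 0.310 (9.9%) with uncorrelated deviations; 0.353 falls to 0.333 (about 5.6%) at correlation 0.8.
- The SE falls by 1 − √(1 − 0.028) = 1.4% to 1 − √(1 − 0.153) = 8.0%.
- The equivalent in patients is 1/(1 − 0.028) − 1 = 3% to 1/(1 − 0.153) − 1 = 18% more for this endpoint.

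**5. Consequence.** Take 7400 randomized (SAP 3), 10% missing at Month 4 (assumed) and residual variance 0.35 (assumed). Then n per arm = 7400 × 0.9/2 = 3330.

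- SE = √(2 × 0.35/3330) = 0.0145. With a 10% cut it is 0.0138.
- The 95% half-width on the ratio, exp(1.96·SE) − 1, goes from 2.88% to 2.73%.
- Power is 1.000 before and after at a ratio of 0.70 (the SAP Appendix B expectation for finerenone, with placebo taken as 1) and at 0.79 (the smallest significant Phase II reduction, 21%). Only near 0.95 does it move, from 0.942 to 0.961.
- In a subgroup of one tenth (333 per arm) the half-width goes from 9.4% to 8.9%.

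**The case against.** The strongest reply is that nothing is wrong. The ANCOVA is valid, its stratum already carries some screening information, the protocol gives a reason for the model (Phase II consistency), and every pre-specified model omits some prognostic variable. The endpoint is also tested only after the primary, the key renal composite, all-cause hospitalization and all-cause mortality have all succeeded (SAP 4.7). All of this stands. It makes the point an optional gain rather than an error, but it is no argument against a covariate that adds no bias and, at this sample size, costs no meaningful precision.

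A reader might infer more than the documents support:

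- **A 17-22% cut in variance.** The equal-correlation formula gives it, but it ignores the stratum already in the model. It also requires Screening to correlate with Visit 1 no more strongly than either does with Month 4, four months later and on drug. No simulated scenario reached 17%.
- **A larger benefit at later visits.** The formula points the other way: with r12 = 0.90 the cut is 9.4% at r1 = r2 = 0.80 and 3.0% at 0.60. The mixed model is also exploratory.
- **Screening never serves as a covariate.** It does where the Visit 1 set is invalid (SAP 4.5.3).
- **Both sets fall on fixed background therapy.** Protocol 6.1 asks only for preferably no adjustment.

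SAP 4.5.4 does not name the model behind the subgroup plots, so the gain there assumes that the same ANCOVA is used.

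**Conclusion.** The point holds as a modest, free gain in precision plus one factual correction. The expected gain is about 3-15% of residual variance (SE about 1-8% lower), shrinking to near zero if correlation simply decays over time. This rests on assumed visit-to-visit noise and correlations that the documents do not give. That screening UACR exists for nearly every patient is inferred from the entry criteria, since no count is stated.

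It does not support a claim that the planned analysis is biased, invalid or underpowered. At the expected effect the overall test gives the same answer with or without the covariate.

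The nesting sentence in SAP 6.2.2.1 is inaccurate on the plan's own terms. Giving the covariate a separate slope in each albuminuria stratum remains legitimate, but baseline UACR does not define that stratum.

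**What to change.** Before unblinding:

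1. Add log screening UACR, combined by the SAP 4.5.3 rule, as a second continuous covariate in the Month 4 ANCOVA (SAP 6.2.2.1) and bring Protocol 10.3.3.3 into line. Add it to the variable list of the Appendix B imputation model. It is optional in the exploratory UACR mixed model.
2. Where a patient has no separate valid Screening set, or the Screening set already serves as baseline, set the covariate equal to log baseline UACR, so that nobody is dropped.
3. Do not fall back on the Run-in set for this covariate, even though SAP 4.1 does so for the strata. It can lie up to 16 weeks before Screening, before background RAS therapy is optimized, and SAP 4.5.1 in general excludes it as a baseline value.
4. Reword the SAP 6.2.2.1 sentence to say that type of albuminuria is defined by Screening UACR.

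The cost is one covariate and its rule in the code, with matching text in the SAP and protocol. No new data are needed. The model would no longer match the Phase II analysis exactly; keeping the current ANCOVA as a sensitivity analysis would preserve that comparison.

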6.2.2.2 Secondary efficacy variables: supportive analysis

The primary analysis of the secondary efficacy time-to-event endpoints will be repeated in the PPS as a supportive analysis. For the PPS analysis, the censoring rules for the primary analysis specified in Section 6.2.2.1 will be further restricted to events occurring up to 30 days after last study drug intake.

Accordingly, subjects with censoring or event date more than 30 days after last study drug intake in the primary analysis will be censored at the date of last study drug intake +30 days.

Subjects with no event up to 30 days after treatment discontinuation will be censored at the date of treatment discontinuation +30 days. For the secondary renal composite endpoints subjects with no event up to 30 days after treatment discontinuation will be censored at the date of their last visit when complete information on all components of the composite renal

endpoint is available, or the date of non-renal death, if this occurred up to 30 days after treatment discontinuation and within 5 months after the last visit with complete information on all components of the composite renal endpoint.

The supportive analyses of the secondary time-to-event endpoints will correspond to those done for the primary composite endpoint in the FAS and PPS (see section 6.2.1.2), except for the tipping point analysis which will only be performed for the key secondary endpoint based on the FAS.

All-cause hospitalization (and sub-categories “CV hospitalization” and “Heart failure hospitalization”) will be further analyzed considering recurrent events by means of the following methods:

- Cumulative incidences based on the Mean Cumulative Function (MCF) to account for recurrent events as described by Doganaksoy and Nelson (1998) [10]
- Andersen-Gill model for first and recurrent events with robust standard errors (identical with Lin Wei Yang and Ying proportional rates model) to test the null hypothesis of the rate ratio for finerenone vs. placebo being equal to 1 [11,12]

Censoring for the recurrent event analysis of hospitalization events will follow the rules as outlined for the time to the first hospitalization event (at the last contact date or date of death and up to the EOS visit).

UACR at Month 4 in the PPS will be analyzed using an ANCOVA as described above. In addition, the following sensitivity analyses accounting for missing data at Month 4 will be conducted:

- On-treatment LOCF approach, only including data up to 30 days after stop of study medication (FAS and PPS).
- Baseline observation carried forward analysis (BOCF), imputing the baseline value for missing data and thus including all subjects with missing Month 4 data with a value of 1 for the ratio of UACR baseline to Month 4 (FAS).
- Multiple imputation analysis (FAS): For reproducibility, the SAS seed number for creating the random numbers will be set to the study (17530). Further details are given in section 9.2.

For all PPS analyses of UACR at month 4, only data up to 30 days after stop of treatment will be considered, all other data will be set to missing before employing the above-mentioned imputation techniques.

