An ‘on-treatment’ analysis will also be performed, repeating the Kaplan Meier estimates and curves as well as the inferential statistics (stratified logrank test and stratified Cox regression model) on the FAS. For the on-treatment analysis, as described for the PPS analysis above, the censoring rules for the primary analysis will be adapted by further restricting to events occurring up to 30 days after last study drug intake.

The logrank test as well as the Cox regression model will also be performed without including stratification factors. The plausibility of the proportional hazards assumption will be assessed by visually examining the plot of the log of the negative log of Kaplan-Meier estimates of the survival function versus log time for evidence of non-parallelism, and by including a treatment by log-transformed time interaction into the Cox model. For the latter, the SAS code is adapted as follows:

```
PROC PHREG DATA = <dataset>;
  MODEL ttevalue * ttecnsr(1) = trtgrpnr trtltime / RL
  TIES=EFRON ALPHA=0.05;
  STRATA {stratum};
  trtltime = trtgrpnr*log(ttevalue);
RUN;
```

The significance of the interaction will be tested at the 5% type I error level. If the interaction is significant and there is strong evidence of non-proportionality from the plots, time-dependent hazard ratios will be estimated with the model that includes the interaction term.

The censoring mechanism of subjects without an event of the primary composite endpoint at the time of analysis is assumed to be non-informative for the primary efficacy analysis. This also implies that the primary analysis is valid under a missing at random (MAR) assumption. Sensitivity analyses will be performed, assessing the impact of a potential informative censoring of subjects lost to follow-up or with withdrawn consent. Non-CV deaths will be treated as censored observations as in the primary analysis.

A summary of the amount of missing data by treatment arm will be given, including number of subjects who have incomplete follow-up on the respective endpoint as well as the ratio of the observed follow-up time to the expected follow-up time for the respective endpoint.

Robustness with respect to missing data will be investigated with a tipping point analysis on the FAS (based on the ITT approach). The analysis will:

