Rationale: The description of the hypotheses was made more accurate by adequately taking into account the stratification factors. At the same time, survival rates were exchanged with hazard rates to create an obvious link from the hypothesis to the hazard ratio which is given as the primary output of the Cox model. However, this exchange has no impact on the content, as survival rates and hazard rates can be translated into each other and the hypotheses of equality of survival rates and of equality of the hazard rates (per stratum) are thus equivalent. Furthermore, the SAS code for the Cox model was corrected to the stratified Cox model specified in the text (by means of adding the stratification factors to the STRATA statement).

Sections affected:

- Section 6.2.1.1: Primary efficacy variable: primary analysis

Modification 12: Modifications and additions to the sensitivity analyses for the primary and secondary efficacy variables

Rationale: The analysis of number of (recurrent) events per 100 patient-years was replaced by an analysis of incidence rate, no longer considering recurrent events because this is not meaningful for the clinical events in this study as most of them usually do not happen more than once. An on-treatment analysis was added for the FAS in line with the protocol. Further supportive analyses were added to check the proportional hazards assumption for the Cox model (plot of the log of the negative of Kaplan-Meier estimates versus log time and Cox model including treatment by log-transformed time as an interaction). More details were given for the tipping point analysis, and it was clarified that this analysis and the newly added on-treatment analysis will only be done for the primary and key secondary renal endpoint based on the FAS.

Sections affected:

- Section 6.2.1.2: Primary efficacy variable: supportive analysis
- Section 6.2.2.2: Secondary efficacy variables: supportive analysis
- Section 9.1: Appendix A: Technical details missing data imputation model for time to event

Modification 13: Censoring rules for on-treatment/PPS analysis of key renal endpoint

Rationale: Censoring rules for the key secondary renal composite endpoint were clarified to consider both the time window of 30 days after treatment discontinuation as usual for this type of analysis in this SAP and the 5 months after the last visit with information of all components of the renal composite endpoint as done for the FAS analysis of this endpoint.

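### SAP 6.2.2.2 gives conflicting censoring dates for the supportive per-protocol analysis of the renal composites: the renal sentence does not carry the 30-day limit over to the last complete visit

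*SAP*

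**What the plan says.** SAP 6.2.2.2 sets censoring for the PPS analysis of the secondary time-to-event endpoints in three steps.

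1. General restriction. The 6.2.2.1 rules "will be further restricted to events occurring up to 30 days after last study drug intake". The section then spells out what this means for later dates: "subjects with censoring or event date more than 30 days after last study drug intake in the primary analysis will be censored", with last intake plus 30 days as the new date. No endpoint is exempted.
2. Event-free subjects, general. "Subjects with no event up to 30 days after treatment discontinuation will be censored at the date of treatment discontinuation +30 days".
3. Event-free subjects, renal composites only. Here "subjects with no event up to 30 days after treatment discontinuation will be censored at the date of their last visit when complete information" exists for every renal component. The alternative date is given by the words "or the date of non-renal death, if this occurred up to 30 days after treatment discontinuation and within 5 months after the last visit", which again means the last visit at which the renal information was complete.

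For the FAS on-treatment analysis, SAP 6.2.1.2 adapts the primary censoring rules by "further restricting to events occurring up to 30 days after last study drug intake". SAP 6.2.2.2 carries the supportive analyses of the primary endpoint over to the secondary ones.

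The change history (SAP 7.1, Modification 13, whose title covers the on-treatment and PPS analyses of the key renal endpoint) says the renal rule was clarified "to consider both the time window of 30 days after treatment discontinuation as usual for this type of analysis in this SAP", together with the 5-month rule. SAP 7.3 records for version 4.0 that the on-treatment and PPS time-to-event analyses are censored at the end-of-study (EOS) visit.

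**The concern.** In step 3 the words about 30 days and 5 months come after the non-renal death. The 5-month part is measured from the last visit, so it can only describe the death. That leaves the visit with no stated limit. Step 3 is also the later and more specific sentence, so a programmer could reasonably code it as an exception to steps 1 and 2.

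Coded that way, the analysis would keep subjects in the risk set after the point at which an event can count. SAP section 3 expects subjects who stop drug to go on attending visits, so complete visits can fall long after the last dose. These subjects can also stay in the PPS: stopping drug is not a validity finding in SAP 5.3, and SAP 6.1.5 calculates compliance only up to the last dose.

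At stake is the PPS result for the renal composites, the first of which is the key secondary endpoint. The FAS on-treatment result is also at stake if it uses the same derivation, as the title of Modification 13 suggests. Both are meant to describe the effect under treatment.

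**Working it through.** **One subject under each rule.** Drug is stopped at Month 6, there is no event, and a complete EOS visit takes place at Month 42 (a study month is 30 days).

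| Rule | Censoring date |
|---|---|
| Steps 1 and 2 | Month 7 |
| Step 3, read alone | Month 42 |
| Step 3 with the 30-day window applied to the visit | Month 6 if a complete premature discontinuation visit took place then, otherwise Month 4 |

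If the same subject has a confirmed 40% eGFR decline at Month 12, the event is excluded under every rule, but step 3 read alone still carries the subject event-free to Month 42. Even on the intended reading the renal date is not last intake plus 30 days. Visits are 4 months apart, and protocol 9.2.9 lets the premature discontinuation visit be omitted. So steps 1 and 2 cannot both stand beside step 3 unchanged.

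**Planning inputs.** The documents attach no figure to this censoring rule. The stopping rate comes from protocol 10.4: 5% per year on finerenone, none given for placebo. As a check on those inputs, a Markov log-rank calculation with uniform accrual, 8% annual placebo events, hazard ratio 0.80, 0.7% annual loss and 5% annual finerenone stopping gives:

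- 972 events and 6235 subjects at 44 months (protocol: 970 and 6212)
- 979 events and 6309 subjects at 48 months (protocol: 976 and 6286)

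**Size under the stand-alone reading.** Let *h* be the renal hazard, *d* the stopping hazard, *g* = 30/365.25 = 0.082 years, and *F* a subject's follow-up, uniform over a range. The value *h* = 0.035 per year is an assumption, since the documents give no renal rate. Loss to follow-up is ignored, and events are taken as observed continuously.

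- On-treatment time for given *F*: T_on = (1 − e^(−hg))/h + e^(−hg) × [1 − e^(−(h+d)(F−g))]/(h+d)
- Share affected (stopped, event-free at stop + 30 days, still followed): e^(−hg) × d/(d+h) × [1 − e^(−(d+h)(F−g))]
- Added off-drug time: T_off = ∫ from g to F of d e^(−d(c−g)) e^(−hc) (F−c) dc

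The counted events are the same under both readings. After averaging over *F*, the rate ratio (stand-alone over capped) is therefore T_on/(T_on + T_off).

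| Follow-up (years) | Stopping per year | Share affected | T_on | T_off | Rate change |
|---|---|---|---|---|---|
| 0.58 to 4.0 (planned, 48 months) | 5% | 9.9% | 2.057 | 0.135 | −6.1% |
| 0.58 to 4.0 | 7% | 13.5% | 2.008 | 0.185 | −8.4% |
| 2.1 to 5.3 (assumed) | 5% | 15.4% | 3.161 | 0.311 | −9.0% |
| 2.1 to 5.3 | 7% | 20.8% | 3.053 | 0.425 | −12.2% |

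The longer range uses the randomization dates in SAP 6.2.4 (October 2015 to January 2019) and assumes that follow-up ended in early 2021.

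**Hazard ratio.** With equal stopping in both arms the two rates fall together and the ratio does not move. If one arm stops at 7% and the other at 5% per year (assumed):

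- Planned follow-up: (1 − 0.0843)/(1 − 0.0614) = 0.976, a shift of 2.4%
- Longer follow-up: (1 − 0.1221)/(1 − 0.0896) = 0.964, a shift of 3.6%

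Both shifts favour the arm that stops more. They are ratios of crude person-time rates, not the planned stratified Cox estimate.

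A separate simulation with a renal rate of 4% per year and an on-drug hazard ratio of 0.82 (both assumed) agrees. The ratio is unchanged with equal stopping. It moves from about 0.82 to 0.81 at 5% versus 4% per year, to 0.80 at 5% versus 3%, and to 0.78 at 10% versus 6%.

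**The case against.** The strongest reply is that 6.2.2.2 does contain a cap. Step 1 covers every secondary time-to-event endpoint, and by it the Month 42 date above becomes Month 7. Modification 13 states that the 30-day window belongs in the renal rule. SAP 6.2.3, written for the exploratory variables, limits PPS analyses to data points and events within 30 days of stopping, and a Month 42 visit lies outside that. For the FAS on-treatment analysis, 6.2.1.2 states the plain 30-day restriction with no renal variant.

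Most of this stands. A reader might infer that the section has no 30-day cap and that the plan counts years off drug as event-free time. The documents do not support that: the cap is written in the general rule and the intent is on record. Nor would the off-drug time be long for most subjects. At 5% per year and planned follow-up, about 6% of finerenone subjects would carry more than one year of it and 2% to 3% more than two.

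A reader might also take step 2 to place censoring after EOS or after death, for example for a completer who stops drug at EOS. That is weak too. The section only restricts 6.2.2.1, which ends at EOS or death, and SAP 7.3 confirms censoring at EOS.

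What the reply does not remove is the contradiction. If the general rule governs, the renal sentence has no function. If the renal sentence governs, its visit has no limit. The change history shows the intent but does not alter the operative text.

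**Conclusion.** The point holds as an internal contradiction in SAP 6.2.2.2, not as a missing cap. Its rules give different censoring dates for the same subject, and the renal sentence does not apply the intended window to the visit. It also mixes two anchors, last study drug intake and treatment discontinuation.

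If the renal sentence were coded as a stand-alone exception, the renal rate would be understated by about 6% at planned follow-up, or about 9% at the longer assumed follow-up. Bias in the hazard ratio requires unequal stopping, about which the documents say nothing for placebo. These sizes rest on the assumed renal hazard, constant hazards, and the protocol's 5% stopping rate applied to either arm.

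Only supportive analyses are touched. The hierarchical FAS tests in SAP 4.7 and 6.2.2.1 are unaffected. It is still worth correcting, because the supportive result for the key secondary endpoint should not depend on a programmer's choice.

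**What to change.** Replace the three steps with one rule per endpoint type, anchored throughout on last study drug intake.

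- **Renal composites:** censor at the last visit with complete information on or before last intake plus 30 days, or at non-renal death if it falls within last intake plus 30 days and within 5 months of that visit. State that this replaces the fixed plus-30-day date, and that the FAS on-treatment analysis uses the same derivation.
- **Other secondary time-to-event endpoints:** censor at the earlier of the 6.2.2.1 censoring date and last intake plus 30 days. No censoring date can then fall after EOS or death, in line with the version 4.0 clarification.

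The cost is a short wording change and one derivation change before unblinding. No new data are needed.
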